11.3.5 Obligation of the Investigator

11.3.5.1 IRB Review

The site PI is responsible for submitting the approved protocol and consent form to the local IRB for review. The IRB must approve all aspects of the study as detailed in the protocol, including the patient informed consent form. It is anticipated that there will be minor site-specific changes in the consent form. The IRB must periodically review the status of the study at appropriate intervals not exceeding one year. The site PI will also be responsible for submitting revisions to the protocol to the IRB, as directed by the DCC, and promptly communicating serious adverse events that result during the study, to both the local IRB and the DCC. After the approval, the informed consent and IRB approval (or amendment) letters must be forwarded to the DCC.

11.3.6 Establishment of Pregnancy Registry

We intend to establish a pregnancy registry for this trial to establish outcomes of pregnancy. Couples who conceive will be offered participation in the Pregnancy Registry and a separate informed consent form will be obtained if they choose to participate. We will track the outcomes of all randomized subjects who have a positive serum pregnancy screen during the course of this study. We will record biochemical pregnancies (defined as positive serum pregnancy screens without ultrasonically detected pregnancies), ectopic pregnancies, and all intrauterine pregnancy losses both before and after 20 weeks including missed abortions, spontaneous abortions, elective abortions, fetal demises, and stillbirths. We will review pregnancy and birth records of the mother and of the fetus to establish neonatal morbidity and mortality and the presence of fetal anomalies. This will be done for all subjects who conceive.

If they participate in the Pregnancy Registry, we will extract from these records concomitant medical and obstetrical conditions, exposure information on all other medical products used, including prescription products, over-the-counter (OTC) products, dietary supplements, vaccines, and insertable or implantable medical devices. We will file individual case reports for all congenital anomalies which will be considered a serious adverse event. Additionally we will provide to the FDA a written annual status report of the pregnancy registry as specified in the guidelines above. We intend at a minimum to perform an annual parent directed screening questionnaire to assess the infant's developmental milestones for the first three years after birth as recommended by the FDA and to review the child's CDC growth curve and medical records. The registry will follow children until age 3. A survey will be administered to the mother annually that will screen for cognitive, and neurodevelopment up to age 3. If medical issues arise from the survey, a medical record review will be performed for more extensive assessment.

11.3.7 Regulatory Requirements

The DCC will work with NICHD staff by providing them with clinical study data, reports, and other support as required for AE Reporting. The Project Managers will work with NICHD colleagues in meeting all regulatory requirements including compliance with ICH and HIPAA requirements, FDA code for federal regulations (Title 21). For example, the DCC Project Managers have registered this clinical trial with ClinicalTrials.gov via a web based data entry system called the Protocol Registration System (PRS) ([NCT02432209](https://www.clinicaltrials.gov/ct2/show/study/NCT02432209)).

11.3.8 Protocol Amendments

Once the protocol is approved by the Steering Committee, it is then reviewed by an Advisory Board and Data and Safety Monitoring Board (DSMB). After all approvals, the DCC will finalize the protocol document that serves as the agreement among all members of the Network. In the meantime, because the DCC administers all patient care costs for the RMN, the DCC will promptly issue subcontracts to the participating sites based on the cost agreements made by the Steering Committee and NICHD.

After the protocols are approved by the RMN and the Steering Committee decides that changes are necessary for scientific or clinical reasons, the DCC will facilitate the procedure in a timely and diligent fashion. The RMN investigators and key personnel will participate in teleconferences and meetings, discuss, vote, and document circumstance and rationales for the changes and the implementation procedure for the changes. These include revising study hypotheses, designs, sample sizes, data entry forms, and appropriate statistical analyses. Once the amendments are finalized and agreed to by the RMN, they will be submitted for IRB and DSMB reviews and approvals.

11.4 Adverse Event Reporting

11.4.1 Serious Adverse Events

All serious adverse events (SAEs) that occur from randomization at Phase I through thirty days after the last dose of study medication (orlistat, clomiphene, or hCG) must be reported or if the patient is pregnant, 6 weeks following delivery. A serious adverse event is defined as: fatal or immediately life-threatening; severely or permanently disabling; requiring or prolonging inpatient hospitalization; overdose (intentional or accidental); congenital anomaly; pregnancy loss after 20 weeks gestation; neonatal death up to 6 weeks after delivery; or, any event adversely affecting the study's risk/benefit ratio. Additionally, any event that, based on appropriate medical judgment, may jeopardize the subject's health and may require medical or surgical intervention to prevent one of the outcomes listed above is considered an SAE.

If an SAE occurs and is thought to be related to the study medication, the study medication will be discontinued.

The site PI will report the SAE by completing and signing the Serious Adverse Event Report Form [available in the "Study Forms" section of the RMN members-only website], and then emailing the document in PDF format to [contact]. Subjects will be identified by study number only. No other identifying information will be included on the form. The site PI must

determine and record on the SAE form whether the SAE is unanticipated or anticipated, and if it is related, possibly related, or unrelated to participation in the research.

DCC staff will enter the SAE information in the central database. The Safety Surveillance team, consisting of the DCC, NICHD research scientist and lead PI of the protocol, will analyze the SAE to determine if it meets the criteria listed in the OHRP 45CFR46 and/or FDA 21CFR312.32 & 3.14.80.

These determinations will dictate timeframes for sites' submission to the DCC, and the DCC's submission to the DSMB (**Table 12**):

[figure not shown]
Table 12: Types of Serious Adverse Events and their reporting requirements

TYPE	SITE	DCC
Unanticipated and related/possibly related SAE, fatal or life-threatening	Report to DCC within 1 business day of discovery	Notify DSMB by end of next business day of receiving site report
Other unanticipated and related/possibly related SAE	Report to DCC within 1 business day of discovery	Notify DSMB 5 business days of receiving site report
Anticipated and related/possibly related SAE	Report to DCC within 5 business days of discovery	Notify DSMB 5 business days of receiving site report
Unrelated SAE (anticipated or unanticipated)	Report to DCC within 10 business days (no more than 3 weeks) of discovery	Notify DSMB within 10 business days (no more than 3 weeks) of receiving site report

Upon receiving notification of an SAE, the DSMB will review it via a closed-session email or conference-call discussion arranged by the NICHD RMN Committee Coordinator [RMN CC] (**Figure 5**). The DSMB will send a report to the RMN CC within two weeks; reports for life-threatening SAEs will be submitted in one week. The DSMB report will include: statement indicating what related information the DSMB reviewed; the review date; the DSMB's assessment of the information reviewed; and the DSMB's recommendation, if any, for the DCC. The RMN CC will then forward the DSMB report to the DCC for the record and appropriate disbursement. The DCC will forward reportable events to all RMN investigators, NIHCD, and the FDA on behalf of the NIHCD if the protocol is under IND. The NIHCD Project Scientist will review, sign, and return the IND safety report to the DCC within 2 business days, and will follow up with the site PI and DCC on the SAE until it is resolved. The Protocol PI will evaluate the frequency and severity of the SAEs and determine if modifications to the protocol and consent form are required. Site PIs will report the SAE to their site IRB according to local IRB requirements. For more information, please see the RMN/DSMB Communication Procedure.

Adverse events deemed non-serious will also be recorded throughout study participation from the start of study drug through one week after the last dose of study medication, and reported to the DCC. If an anticipated serious adverse event occurs at a frequency greater than expected, the DCC will notify the DSMB by the end of the next business day of discovery and follow the procedures for reporting serious and unanticipated and related adverse events. The DCC will forward relevant safety information to the DSMB. If an adverse event not initially determined to be reportable to the FDA under 21CFR312.32 is so reportable, the DCC will report the adverse event to the FDA within 15 calendar days after the determination is made.

Figure 5: Serious Adverse Event Flow Chart

CFR= Code of Federal Regulations

12 Human Subjects

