6.1.1 Determine Baseline Physical Activity

Subjects will be dispensed a Fitbit Physical Activity monitor during the randomization visit which will be used to determine average daily steps over a week's time.

Standard Physical Activity Intervention: This will be identical to the physical activity described above for the intensive physical activity group. There will be no dietary recommendations, no use of meal replacements, and no use of anti-obesity drugs. Subjects will have the same monitoring schedule both on site and off site as subjects in the intensive lifestyle modification.

Conception during Lifestyle Modification We will encourage intercourse without barriers during the lifestyle modification phase and welcome any pregnancies which happen. They will be managed identically as though that occur during the empiric infertility treatment phase of this study (Phase II below). Of course such pregnancies will be analyzed by treatment group according to intention-to-treat (ITT) principles. We are using safe and widely utilized lifestyle modifications. We are using an OTC weight loss drug, Alli, that has no known early adverse pregnancy effects and we will immediately discontinue it if pregnancy occurs. The ability to conceive at all points in this study will increase the appeal to participate and also the external validity of our results. No one with infertility wants to stop attempting pregnancy as part of infertility treatment. This also led us to reject using the oral contraceptive pill as a control arm for unexplained infertility.

Phase II – Standardized infertility treatment

After completion of Phase I (or 16 weeks of pretreatment), all subjects will enter Phase II. This phase will be universally administered to all participants in an open label, but standardized fashion. In this part of the study, subjects will receive three cycles of ovarian stimulation/hCG

trigger for ovulation/ timed IUI and followed by midluteal visit. We will clamp weight and activity in both groups and continue to monitor with the Fitbit and the Aria scale. We will modify and streamline the study procedures from our AMIGOS study.

Phase III – Pregnancy

There will be no treatment intervention during pregnancy, though we will continue to monitor weight and have trimester study visits.

Phase IV – Pregnancy Registry

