7.1 Schedule of Evaluations

The table below (**Table 7**) summarizes the clinical and laboratory evaluations during the trial. A description of the visits follows.

Table 7: Study Visits and Procedures

Phases	Phase 1: Lifestyle Intervention (16 weeks)				Phase 2: Infertility Treatment						Phase 3: Pregnancy	
	Visit Titles	Screen (can be done in 2 visits)	Baseline /Drug Assign	Month Visit 1, 2 & 3	End of Phase 1 (week 16)	Cycle 1 Baseline (day1-5 of menses)	Monitor Visit *(cycle day 8-12)	IUI	Urine Preg Test **	Serum hCG ***		End of Phase 2
Informed Consent	X											
Medical Assessment	X											
Vital Signs & Biometrics	X	X	X	X	X						X	X
Complete Physical Exam	X											
Gynecological Exam and pap smear	X											
Acne/Hirsutism Assessment	X				X						X	
Transvaginal ultrasound	X				X	X						
Sonohysterogram or Hysterosalpingogram	X											
Questionnaires & QOL surveys	X				X						X	
Urine pregnancy test	X			X	X	X			X (@home)			
Serum pregnancy test										X		
Blood work for Rubella, Varicella, HIV, genetic tests and hgb electrophoresis (optional)	X											
Blood work for female hormones	X											
Blood work for safety labs, lipid panel and HgbA1C	X				X						X	
Blood work for central core	X	X	X	X	X						X	X
Blood work and urine for reserve ancillary studies (optional)	X	X	X	X	X						X	X
Blood work for Whole blood (optional)			X									
Blood work for RMN Repository (optional)			X									
Vaginal Swab	X				X							X
Rectal swab	X				X							X
Saliva sample (optional)			X		X							
Dispense meds			X	X		X		X				
Collect meds				X	X		X				X	
Order meal replacements (if applicable)			X	X								
Dispense Fitbit and Aria scale			X									
Dispense diaries			X	X		X		X				
Collect diaries				X	X		X				X	
Adverse Events & Concomitant Meds			X	X	X	X	X		X		X	X
Intrauterine Insemination								X				
MALE PROCEDURES												
Informed Consent	X											
Medical Assessment	X											
Vital signs & Biometrics	X										X	
Questionnaires & QOL surveys	X										X	
Semen analysis/collection	X							X				
Semen for RMN Repository (optional)	X											

Blood work and urine for RMN repository (optional)	X										
Saliva sample (optional)	X										

*Monitor visits will be repeated on an individual basis until hCG administration

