9.1 Phase I

There are no predetermined criteria for discontinuation during Phase I. Subjects will be allowed to continue in the trial even if they do not achieve the goals of the two interventions and eventually receive the infertility treatment in Phase II. However each subject will have to complete the 16 week pretreatment period before receiving the Phase II treatments. Subjects can not be accelerated into Phase II.

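### Section 11.4.1 starts non-serious AE recording with a study drug that the standard arm does not take in Phase I, and Table 12 and the DSMB Charter set different timelines for some fatal or life-threatening SAEs

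*Combined protocol and SAP*

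**What the plan says.** Section 11.4.1 sets two windows. Non-serious events are "recorded throughout study participation from the start of study drug through one week after the last dose of study medication". SAEs that occur "from randomization at Phase I through thirty days after the last dose of study medication (orlistat, clomiphene, or hCG) must be reported"; if the woman is pregnant, SAE reporting runs to six weeks after delivery. The three drugs in that parenthesis are the section's only list of study medication.

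For the standard arm in Phase I, section 6.1.1 says: "There will be no dietary recommendations, no use of meal replacements, and no use of anti-obesity drugs". It adds: "Subjects will have the same monitoring schedule both on site and off site as subjects in the intensive lifestyle modification". Section 9.1 requires everyone to complete 16 weeks before fertility treatment: "Subjects can not be accelerated into Phase II".

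Table 7 has one row, "Adverse Events & Concomitant Meds", with no split by arm. In section 7.2, the lists for the monthly Phase I visits and the week 16 closeout each include adverse event collection for all subjects.

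On reporting to the DSMB, Table 12 sets limits by relatedness and expectedness, counted from discovery by the site. Only its top row singles out fatal or life-threatening events. Section 1 of the DSMB Charter (Appendix P) gives one week, counted from the event, for any fatal or life-threatening SAE.

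**The concern.** Phase I is the only phase in which the arms are treated differently, so it is where a comparison of tolerability matters most. Section 2.1 makes tracking safety in every phase part of the primary aim, and section 10.9 includes adverse events among the binary outcomes to be modelled. Section 8.1.1 expects musculoskeletal pain from increased activity, which both arms undertake. If such events are recorded from the first orlistat dose in one arm and not until clomiphene in the other, the intensive arm will look worse because of the recording rule.

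The drug-based end points raise a second problem. Women can take part in the trial without ever taking a listed drug, and for them a window that ends a fixed time after the last dose has no end.

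The third problem is oversight. The data coordinating center could meet every limit in Table 12 and still miss the Charter's limit for a death or a life-threatening event.

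**Working it through.** **Non-serious window.** No arithmetic is needed; the texts are set side by side.

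1. Recording opens when study drug starts (11.4.1).
2. Study medication is orlistat, clomiphene or hCG (11.4.1).
3. The standard arm has no anti-obesity drug in Phase I (6.1.1) and cannot reach clomiphene or hCG before week 16 (9.1).
4. From 1 to 3, read literally, the standard arm's window is closed for all 16 weeks of Phase I. The intensive arm's opens with orlistat.
5. Table 7, the Phase I visit lists and the shared monitoring schedule collect events in both arms over those 16 weeks. Table 7's columns are partly displaced in the text available here, but the visit lists establish Phase I collection independently.
6. The SAE window opens at randomization in both arms. Only the non-serious rule is tied to drug.

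**End of the windows.** A standard-arm woman who leaves before Phase II has no last dose of a listed drug. Thirty days after it (SAEs) and one week after it (non-serious events) are both undefined. If she conceives in Phase I, which section 6.1.1 allows for ("We will encourage intercourse without barriers during the lifestyle modification phase and welcome any pregnancies which happen"), her SAE window is defined, because it runs to six weeks after delivery. On the literal reading, her non-serious window never opens.

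**DSMB timelines.** Inputs: Table 12 for the site and coordinating-center steps; Charter section 1 for the one-week limit. Business days are converted to calendar days from a weekday start with no public holidays. Discovery is assumed to fall on the day of the event; later discovery widens each gap.

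| Fatal or life-threatening SAE | Site + coordinating center (business days) | Calendar days from discovery | Less Charter's 7 |
|---|---|---|---|
| Unanticipated, related or possibly related | 1 + 1 = 2 | 2 to 4 | within the limit |
| Anticipated, related or possibly related | 5 + 5 = 10 | 14 | 14 − 7 = 7 over |
| Unrelated | 10 + 10 = 20 | 28 | 28 − 7 = 21 over |

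The time for the DSMB's own report also differs. Section 11.4.1 gives one week for life-threatening SAEs. The Charter gives 7 business days for life-threatening or fatal ones, which is 9 calendar days from a Monday to Wednesday start and 11 from a Thursday or Friday.

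**The case against.** The best defense is that the literal reading is the weaker one. The sentence itself says that recording runs throughout participation. Table 7 gives everyone a visit titled "Baseline /Drug Assign". Folic acid goes to all subjects in all phases (6.1), prenatal supplementation is mentioned with the study interventions (6.2), and prenatal vitamins are dispensed at randomization and at monthly visits (7.2). Section 8.1.1 lists vitamin side effects beside those of orlistat, and the monthly and closeout visits collect leftover medication without naming an arm. If vitamins count as study drug, both windows open together.

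Much of this stands, and it makes the rule ambiguous rather than plainly one-sided. It does not settle the matter. Vitamins are not in the section's drug list, and section 6.4 ties Phase I pill counts to the intensive program. Counting folic acid would also move the end of the window, since supplementation continues through every phase. The protocol does not say whether 11.4.1 or the visit lists govern.

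It is also fair that non-serious events are not a named secondary outcome in section 10.3.2, and that section 10.9 mentions adverse events only as an example of rare binary events. That limits the weight of the point.

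On timelines, the limits are maxima, so meeting the shorter one satisfies both texts. Part of the Charter, Figure 5 and the separate RMN/DSMB communication procedure could not be seen and might resolve the difference. Table 12's three-week caps could be added to give 42 days for unrelated events, but that stacks two parenthetical limits on a 10 + 10 business-day rule and is not relied on here.

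**Conclusion.** The inconsistency is real and should be fixed, with limited consequences. On the literal reading, the standard arm's non-serious events are outside the window for all 16 weeks of Phase I, for 190 planned women. That is the full extent of one of two readings, not an estimate of lost data. The number of events affected cannot be derived, because it depends on which rule sites and CRF instructions follow. If all follow the visit lists, there is no bias.

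A reader might infer that the trial will not collect Phase I adverse events in the standard arm, or that its safety comparison is biased. The documents do not support that: the visit-level instructions collect events in both arms, Phase I SAEs are captured from randomization, and the primary outcome does not depend on this rule. Nor do standard-arm women who conceive in Phase I drop out of SAE reporting, since the pregnancy rule covers them. The undefined SAE end applies only to non-pregnant women who never take a listed drug, and the documents do not say how many to expect.

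The timeline conflict covers fatal or life-threatening SAEs that are anticipated and related (at least 7 days beyond the Charter at the limit) or unrelated (at least 21 days). It does not extend to unanticipated related ones, where Table 12 fits the Charter if discovery is prompt. This part is subject to the unseen Charter text, Figure 5 and communication procedure.

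**What to change.** 1. In section 11.4.1, start non-serious adverse event recording at randomization in both arms, to match the SAE window and the Phase I visit lists.
2. For non-pregnant women who never take a listed drug, define an end to the non-serious and SAE windows that gives equal length of follow-up in both arms. Stopping a standard-arm woman at withdrawal while an intensive-arm woman keeps 30 days after her last orlistat dose would create a new imbalance. Leave the existing rule, SAEs to six weeks after delivery, unchanged for every woman who conceives.
3. Reconcile Table 12 and the DSMB review times in section 11.4.1 with the Charter, so that fatal and life-threatening SAEs have one timeline with one clock start, either event or discovery.

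The cost is protocol and Charter wording plus CRF instructions. The Phase I visits that collect the data are already scheduled in both arms. Depending on the end point chosen under item 2, a follow-up contact may be needed for women who leave early.

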12.1 Institutional Review Board (IRB) Review and Informed Consent

This protocol and the informed consent document (see Appendix) and any subsequent modifications will be reviewed and approved by the IRB responsible for oversight of the study. A signed consent form will be obtained from the subject. The consent form will describe the purpose of the study, the procedures to be followed, and the risks and benefits of participation. A copy of the consent form will be given to the subject, parent, or legal guardian, and this fact will be documented in the subject's record.

